### **6.8. Antimalarial treatment**

Treatment will be provided based on body weight (Appendix B). Blood schizonticide for any species is 3-day DHA-PP (daily dose: 6-10 kg=1/2 tab, 11-17 kg=1 tab, 18-30 kg=1 ½ tab, 31-40 kg=2 tab). For *P. vivax* subjects, the administration of high dose primaquine will be started at the same day of DHA-PP treatment (see Table 2 appendix B for PQ dosage). Meal should be given prior to PQ administration daily. The total dose of PQ should be completed within 10 days as the window period. Subjects who does not complete the dose will be recorded, and still be followed until end of study. Monitoring of Hb level and hemoglobinuria for treated subjects will be done daily before and during treatment by Hb measurement using HemoCue (HemoCue AB, Angelholm, Sweden) and urine test (inspection and urinalysis) in order to detect hemolysis. Primaquine will be stopped if hemolysis

occur, the subject will be observed for daily vital sign, Hb level, and urine until recovery. If worsen, the subject will be referred to the hospital for further management, and given blood transfusion if necessary (Appendix E).

Primaquine for *P. falciparum* will be given as single dose 0.25 mg/kgBW (6-17 kg=1/4 tab, 18-30 kg=1/2 tab, 31-40 kg=3/4 tab). *P. ovale* will be treated as *P. vivax*. Mixed infection with *Pv* will be treated as *Pv*.

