### 6.3. Study design and study overview

The study design is a randomized controlled trial with serological screening and treatment as the intervention. Selected schoolchildren will be allocated into two study arms: (1) serological screening and treatment (SSAT), and (2) routine care as control arm.

At enrolment, in the SSAT arm, individuals found *P. vivax* positive by either serological (Luminex) or Giemsa stained microscopic examination regardless of the symptoms will receive supervised treatment (direct observation) with high dose PQ (daily 1 mg/kg BW) for 7 days ( $P_o=P_v$ ). In the control arm, only symptomatic individuals found *P. vivax* positive by Giemsa stained microscopic examination will receive the same regimen ( $P_o=P_v$ ). In addition, in the treated children of both arms, dihydroartemisinin-piperaquine (DHA-PP) will be given as blood schizontocide according to body weight. All other species (*P. falciparum*, *P. malariae*) found by Giemsa stained microscopic examination will be treated according to national guideline. Serological examination will be performed by Luminex (done at Eijkman, Jakarta) and point-of-care (POC) antibody detection using rapid test on site

Follow up will be performed monthly for 9 months. During this period, 400  $\mu$ L of finger pricked blood samples will be collected from all children in both arms. These samples will be tested for malaria presence by PCR which will be done at EO CRU, Jakarta. However, children with clinical symptoms (body temperature of  $\geq 37.5^\circ\text{C}$  and/or history of fever within 3 days), will be examined by Giemsa stained microscopy on site, and treated if positive (any species) according to national guideline (unsupervised).

At the last follow up, a mass blood survey will be conducted to both arms for *Pv* serological test, LMF, and PCR. Those found positive by LMF for any species will be treated regardless of their symptoms.

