### **6.7. Follow up and end of study**

First follow up will be conducted one month after the last dose of PQ treatment administration. Every visit, blood samples from finger prick and skin (LMS) will be taken. Unlike in the 16ecurrent process, malaria blood smear will be made only from participants with clinical symptoms suggestive for malaria. If positive, they will be treated. All treatment during follow up period will be provided by PHC staff according to national guideline (Appendix B table 1 & 3).

At the end of study (month-9 of the follow up), mass blood survey will be conducted to collect finger prick blood (LMF, Pv serological test, qPCR) and LMS. Seroconversion will be assessed. All LMF (+) will be treated as above.

All study subjects will be followed until the end of study (month 9) although they cannot fulfil the complete schedule.

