**Table 3. Low dose Primaquine**

Single 0.25 mg/kg BW dose PQ will be given for *P. falciparum* or 14 days 0.25 mg/kg BW dose PQ for *P. vivax/P. ovale* infection any time during the study period.

Day	Species	Daily dosage based on body weight					
		≤ 5 kg	6-17 kg	18-30 kg	31-40 kg	41-59 kg	≥ 60 kg
1	P. falciparum	-	¼	½	¾	1	1
1-14	P. vivax/P. ovale	-	¼	½	¾	1	1

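### Section 6.8 and the Table 3 text each assign a primaquine regimen to P. vivax without the time-point limit used elsewhere, so some cases fall under two regimens

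*Protocol*

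**What the plan says.** - **6.3 (Study design), enrolment.** Children in the SSAT arm who are positive for *P. vivax* by serology or slide "will receive supervised treatment (direct observation) with high dose PQ (daily 1 mg/kg BW) for 7 days". In the control arm only symptomatic, slide-positive children get the same course. The synopsis agrees. Appendix I, which covers enrolment only, lists the 7-day course for slide-positive *P. vivax* and *P. ovale*.
- **6.3 and 6.7, follow-up.** Symptomatic slide-positive children are treated under the national guideline, unsupervised. Section 6.7 names the tables: "All treatment during follow up period will be provided by PHC staff according to national guideline (Appendix B table 1 & 3". Table 2 is not among them.
- **6.8 (Antimalarial treatment).** This section sends *P. vivax* subjects to the doses of Table 2: "the administration of high dose primaquine will be started at the same day of DHA-PP treatment". No time point, arm or setting is given. *P. ovale* is brought under the same rule, and "Mixed infection with *Pv* will be treated as *Pv". The section adds "The total dose of PQ should be completed within 10 days as the window period", and asks for daily haemoglobin and urine checks in treated subjects.
- **Appendix B, Table 3.** The text assigns "14 days 0.25 mg/kg BW dose PQ for" *P. vivax* or *P. ovale* "infection any time during the study period". Enrolment is not excluded.

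**The concern.** Section 6.8 is the general treatment section, and Appendix B holds the dosing tables that staff will have in hand. Both state a scope wider than the split by time point. A person working from 6.8 alone would use Table 2 for a follow-up case. A person working from Table 3 alone would use the 14-day course for a slide-positive case at enrolment.

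Three things depend on the answer:

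- **The intervention.** At enrolment the supervised 7-day course is the treatment half of what the trial tests.
- **The outcome counts.** Section 8.3 counts *P. vivax* recurrences over person-time, including multiple recurrences. The regimen given for one episode can affect later counted events in the same child.
- **Safety.** Endpoint VI concerns adverse events of high-dose primaquine, so the regimen decides who is exposed. It also bears on which children get daily checks for haemolysis.

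**Working it through.** **Step 1: the passages side by side.**

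| Case | Time-point passages | 6.8 as worded | Table 3 text as worded |
|---|---|---|---|
| Slide-positive *P. vivax*/*P. ovale*, treated at enrolment | 1 mg/kg × 7 days, supervised (synopsis, 6.3, Appendix I) | Table 2, high dose | 0.25 mg/kg × 14 days |
| Treated on serology alone, SSAT arm, enrolment | 1 mg/kg × 7 days, supervised (synopsis, 6.3) | No conflict | Not covered: the text speaks of infection, not serology |
| *P. vivax* treated in follow-up | Tables 1 and 3, unsupervised (6.3, 6.7) | Table 2, high dose | 0.25 mg/kg × 14 days |

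The first row conflicts because of Table 3's wording, and the third because of 6.8's. The middle row has no conflict. Table 1 shows that scope can be stated plainly: it says that its dosage holds both at enrolment and in follow-up. Tables 2 and 3 make no such split.

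**Step 2: how far apart the regimens are.**

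Daily dose (mg/kg) = tablets × 15 mg / body weight. Course total = daily dose × 7 (Table 2) or × 14 (Table 3). Table 3 gives no tablet strength, so 15 mg is assumed from Table 2.

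- Reproducing Table 2 at 15 kg: 1 × 15 / 15 = 1 mg/kg per day, and × 7 = 7. This matches the table. The total column is headed mg, but its values are mg/kg. All rows from 12 to 45 kg reproduce on that basis.
- Nominal totals: 1 × 7 = 7 mg/kg and 0.25 × 14 = 3.5 mg/kg. Total ratio 7 / 3.5 = 2; daily ratio 1 / 0.25 = 4.
- Narrowest gap, 18 kg: Table 2 gives 1.25 × 15 / 18 = 1.04 mg/kg daily, total 7.29. Table 3 gives 0.5 × 15 / 18 = 0.417 daily, total 5.83. Ratios 1.25 (total) and 2.5 (daily).
- Widest gap, 17 kg: Table 2 gives 1.25 × 15 / 17 = 1.10 daily, total 7.72. Table 3 gives 0.25 × 15 / 17 = 0.221 daily, total 3.09. Ratios 2.5 and 5.
- Over 12 to 45 kg, totals run from 6.18 to 9.13 mg/kg (Table 2) and from 3.09 to 5.83 mg/kg (Table 3).

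**Step 3: the window and the checks.**

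- A 14-day course cannot finish in 10 days, and an unsupervised course does not fit daily checks. Both clashes arise only if 6.8's instructions are carried over to Table 3 courses. The section does not say whether they are.
- Appendix H places primaquine on D1–D7 and HemoCue and urine checks on d0–d7, with none of these in the monthly columns. Section 6.9 ties adverse-event observation to a 7-day schedule.
- The treatment case report form has 14 day-columns, lists haemoglobin only at D-1 and D-3 and urine only at D-1, and serves both school and family screening. It matches neither 6.8 nor Appendix H on monitoring.

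**Step 4: how many courses.** The protocol gives no expected number of treated follow-up episodes. Assuming that 5% to 15% of 700 children (2 × 350) are treated once, 0.05 × 700 = 35 to 0.15 × 700 = 105 courses would fall under both texts. That is not a count of courses that would go wrong.

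**The case against.** The best defence is that the rule by time point is explicit and repeated in the synopsis, 6.3, 6.7 and Appendix I, and that specific passages govern general ones. Section 6.8 cites Table 2, so its meal, window and daily checks read naturally as instructions for that course, and Appendix H supports this. The Table 3 sentence also covers the single *P. falciparum* dose, which is given both at enrolment and in follow-up, so its open time scope fits that half.

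Most of this stands as evidence of intent, and it rules out several stronger readings:

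- A reader might infer three rival regimens. The documents support one inferable rule and two passages that overrun it. Section 6.8 never claims to cover every *P. vivax* case; it is unrestricted by omission.
- A reader might infer that Table 3 could change treatment for children treated on serology alone. Its text is about infection and does not reach them.
- A reader might count the 10-day window against the 14-day course as a separate contradiction. It depends on applying 6.8 to Table 3 courses.
- A reader might infer that exposure to the high dose cannot be established. The treatment form already records dates and daily tablet counts.
- A reader might infer bias between arms. A common rule for treating recurrences acts more often in the arm with more of them however 6.8 is worded, and treatment at the month-9 survey cannot alter events within follow-up.

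What the defence does not remove is that the general treatment section and the dosing table still state a scope that the other passages contradict, on a point that touches the intervention and haemolysis monitoring.

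**Conclusion.** The concern holds as a defect of scope in two passages. As worded, 6.8 reaches follow-up cases that 6.7 places under Table 3, and the Table 3 text reaches slide-positive enrolment cases that 6.3 and Appendix I place on the 7-day course. The regimens differ nominally 2-fold in total and 4-fold in daily dose. By the tablet tables the ratios are 1.25 to 2.5 and 2.5 to 5, assuming 15 mg tablets in Table 3. The coverage of the 10-day window and daily checks is not stated, and the treatment form disagrees with 6.8 on monitoring.

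The number of courses at risk cannot be derived from the protocol, and the conclusion does not rest on one. The trial design is not in question. The point is more than clerical because it concerns dosing and monitoring text that staff will follow. No view is taken here on which regimen is right.

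**What to change.** - The sponsor should reconcile 6.8 and the texts of Tables 2 and 3 with 6.3, 6.7 and Appendix I, so that each names the time point it covers. The regimen is for the clinical investigators to decide.
- Section 6.8 should state which courses the 10-day window and the daily haemoglobin and urine checks apply to. Appendix H and the treatment form should be brought into line with that statement.
- Safety endpoint VI should be analysed in children who received the high-dose course, identified from the dates and daily tablet counts on the treatment form. These need to be read with body weight, which the screening and follow-up forms hold: one tablet a day is the Table 2 dose at 13 to 16 kg and the Table 3 dose from 41 kg.

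The cost is protocol wording, alignment of one form and one sentence on the safety population. No patients or visits are added.

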### **6.9. Adverse Event (AE) and Serious Adverse Event (SAE)**

Adverse events (AE) are defined as any untoward and unintended reaction during the study period. AE will be identified and recorded in CRF by field team in collaboration with the teachers and primary health center attendants. These subjects will be given symptomatic treatment as necessary. Specific AE are black urine, gastro intestinal disturbances, blue lips and breathless.

Serious adverse events (SAE) is an AE which becomes serious and could endanger the life of subjects, cause hospitalization/prolong hospitalization, and disability to conduct normal life. The SAE will be recorded in SAE form and reported to PI, clinician coinvestigators, Ethic Committee, and DSMB within 24 hours. SAE' subjects will be treated in RSPP/RS Atambua until recover completely. Complete SAE report will be distributed within one month after the occurrence of SAE.

The observation of AE and SAE will be performed routinely according to the schedule of drug administration (7 days).

If subject is allergic to DHA-PP, second-line treatment (7 days quinine) will be provided by the team in close collaboration with local primary health center (11-17 kg: 3x1, 18-33 kg: 3x1½, 34-40 kg: 3x2). All treatments for AE/SAE which will be given either at the PHC or in hospital, should be reported to the investigator team and being documented in the database.

Treatment will be stopped immediately if any of these following occurs: 1) allergy to the antimalarial regimen being given, 2) Hb drop of more than 20%, 3) active hemolysis which is proven by urine test and Hb drop, 4) Hb drop with warning sign of MetHb (breathless, blue lip/cyanosis, drowsiness, lethargy, palpitation), 5) Any possible SAE related to antimalarial treatment. Hospitalisation is indicated for 2) to 5).

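### Sections 6.8 and 6.9 give different admission instructions for a stable child with proven haemolysis on primaquine; secondarily, the listed urinalysis has no chemical test for haemoglobin

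*Protocol*

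**What the plan says.** Section 6.8 of the protocol sets the monitoring of treated children: "Monitoring of Hb level and hemoglobinuria for treated subjects will be done daily before and during treatment", using HemoCue and a "urine test (inspection and urinalysis) in order to detect hemolysis". The response begins "Primaquine will be stopped if hemolysis" occurs. After that, "the subject will be observed for daily vital sign, Hb level, and urine until recovery". Hospital comes in only with the next step: "If worsen, the subject will be referred to the hospital for further management". That sentence ends with a reference to Appendix E.

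Section 6.9 lists five events that stop treatment at once. Criterion 2 is an "Hb drop of more than 20" per cent. Criterion 3 is "active hemolysis which is proven by urine test and Hb drop". Criterion 1 is drug allergy, criterion 4 is an Hb fall with signs of methaemoglobinaemia, and criterion 5 is any possible treatment-related SAE. The section then says "Hospitalisation is indicated for 2) to 5"). It also counts an event that causes or prolongs a hospital stay as an SAE. SAEs are reported within 24 hours to the ethics committee and the DSMB, among others, and the child is treated in named hospitals until fully recovered.

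Appendix H schedules urine colour inspection and urinalysis on d0 to d7. Its footnote 2 gives the urinalysis three components: macroscopic appearance, protein as the only chemistry, and microscopy for red cells.

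**The concern.** High-dose primaquine can cause haemolysis, and section 9.1 relies on G6PD screening and daily haemolysis monitoring as the safeguards. In the SSAT arm the drug also goes to seropositive children without symptoms, so field staff need one rule for what to do when haemolysis is found. Sections 6.8 and 6.9 attach different actions to it: one observes and refers on worsening, the other admits.

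The first stake is the child's care. The second is the safety record. Admission is one of the routes to an SAE, so the section that a team follows can decide the label and whether 24-hour reporting applies. AEs and SAEs of high-dose primaquine are secondary endpoint VI, and section 8.3 reports their type and number.

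The urine point is linked but smaller. Criterion 3 requires urine proof, section 6.8 names haemoglobinuria as what is monitored, and the listed urinalysis does not measure it chemically.

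**Working it through.** The plan gives no figure to reproduce here. The check sets the texts side by side and then sizes the gap left by the urine test.

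**Admission rule.** Inputs: sections 6.8 and 6.9.

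| Child on primaquine | Section 6.8 | Section 6.9 | Consistent? |
|---|---|---|---|
| One signal only (urine finding, or Hb fall of 20% or less), stable, no other criterion met | Stop if judged haemolysis; observe | No criterion for admission met | Yes |
| Urine test and Hb fall both present (criterion 3), stable | Stop; observe; refer only on worsening | Stop; hospitalise | **No** |
| Criterion 3 met and worsening | Refer to hospital | Hospitalise | Yes |

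The clash is in the second row. Three features of the wording put it there:

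1. A child meeting criterion 3 has haemolysis shown by the two tests that 6.8 uses to look for it, so that child falls under 6.8 as well.
2. Criterion 3 sets no minimum Hb fall. A stable child with a positive urine test and, for illustration, a 10% fall meets it.
3. Of the five stop criteria, four (2 to 5) indicate hospitalisation in 6.9, and none of the four carries the worsening condition of 6.8.

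Criteria 2, 4 and 5 are not worded as proven haemolysis, so the clash is shown directly only for criterion 3.

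**Urine test.** Inputs: criteria 2 and 3 in 6.9; the 9 g/dL Hb entry limit in 6.4; Appendix H footnote 2. The protocol gives no typical baseline Hb, so 11 and 13 g/dL are assumptions.

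Criterion 2 needs a fall of more than 20%. The largest fall that does not meet it is baseline × 0.20:

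- Entry limit: 9.0 × 0.20 = 1.8 g/dL, so Hb down to 9.0 − 1.8 = 7.2 g/dL.
- Assumed 11.0: 11.0 × 0.20 = 2.2 g/dL, down to 8.8 g/dL.
- Assumed 13.0: 13.0 × 0.20 = 2.6 g/dL, down to 10.4 g/dL.

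Within that range, with no methaemoglobinaemia signs and no possible SAE, criterion 3 is the only numbered criterion that indicates admission, and it depends on the urine test. Appendix H schedules 8 urinalyses (d0 to d7), each with 3 listed components. Protein is not specific for haemoglobin, and red-cell microscopy shows intact cells, not free haemoglobin. What remains is visible colour. Haemoglobinuria too slight to see could therefore leave criterion 3 unmet.

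**The case against.** The strongest reply is that 6.8 sends the reader to Appendix E at exactly this step. The steps of that appendix are not visible in the text available, and they may contain a tiered response. Their absence here is no fault of the plan, and a reader should not infer that the protocol lacks a haemolysis pathway. This stands. It does not remove the difference in wording: whatever Appendix E says, someone acting on 6.8 alone and someone acting on 6.9 alone would handle the stable criterion-3 child differently.

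A second reply is that 6.8 covers haemolysis in general, including a single signal, while criterion 3 is the narrower case needing both tests. On that reading most children get consistent instructions, and 6.9 governs the rest as the more specific and more protective rule. This is plausible and probably the intention. But 6.8 sets no severity limit and does not refer to 6.9, so the reader has to supply the hierarchy.

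On reporting, a reader might infer that events would be lost or SAE counts made unreliable. The documents do not support that. Section 6.9 requires treatment for AEs and SAEs, at the health centre or in hospital, to be reported to the investigators and documented. Admission is also not the only route to an SAE, since danger to life and disability count too. Only the label and the 24-hour report can differ, and only where no other seriousness criterion applies.

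On urine, a reader might infer that haemolysis would go unnoticed or primaquine be continued. That is not supported either. Section 6.8 stops the drug for haemolysis without asking for urine proof. Visibly dark urine with an Hb fall can meet criterion 3. Daily HemoCue, daily colour inspection, criteria 2, 4 and 5, and the falling-haemoglobin trigger in Appendix E all remain.

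**Conclusion.** The inconsistency is real but narrow. It concerns a child who meets criterion 3 of section 6.9 and does not worsen: 6.8 says observe, 6.9 says hospitalise. It can change that child's care and, absent another seriousness criterion, the AE/SAE label and 24-hour reporting. How often this would happen cannot be stated, because the protocol gives no haemolysis rate, and children below 70% G6PD activity are excluded. The conclusion rests on the wording of 6.8 and 6.9 alone and assumes nothing about the unseen steps of Appendix E.

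The urine point is a secondary safety improvement. It bears on admission in one corner: haemoglobinuria that is not visible, an Hb fall of 20% or less (up to 1.8 g/dL at the entry limit, 2.2 to 2.6 g/dL at the assumed baselines), and no other criterion met. Stopping primaquine under 6.8, the primary analysis and power are untouched. The point should be fixed because children's safety is involved and the change is small; it does not threaten the trial's main result.

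**What to change.** 1. Amend 6.8 to read along these lines: *Primaquine is stopped if haemolysis occurs. A child meeting any of criteria 2 to 5 in section 6.9 is hospitalised. A child with suspected or milder haemolysis who meets none of them is observed daily (vital signs, Hb, urine) until recovery, and referred if the condition worsens.* Check Appendix E and make it state the same rule.
2. In Appendix H footnote 2, change the chemistry entry to *chemistry (protein, blood/haemoglobin)*. The red-cell microscopy already listed helps to separate haematuria from haemoglobinuria when the strip is positive.

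The cost is a wording change in 6.8, a check of one appendix, one footnote, and a strip with a blood field on urine that is already tested daily. The downsides are possibly more admissions than under 6.8 as it stands, and some false-positive strips from haematuria.

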### **6.10. Gametocyte study**

At enrollment, blood samples will also be taken from shallow vasculature of the skin from the ankle of all participants from both arms for microscopic examination (light microscopic-skin/LMS) (figure 2). Malaria status by LMS will be assessed post-hoc and will not indicate any treatment.

To determine longevity of these skin gametocytes, LMS samples will be taken at monthly follow up. Moreover, to explore any diurnal variation of this stage, we should obtain blood samples at night and during the day. Therefore, during follow up activity, house visit will be made to the malaria infected children with symptoms for collecting two times blood samples, i.e. 7-10 AM and 7-10 PM. In addition, household members will be asked to contribute their blood samples (LMF, LMS, and PCR). For the household members, LMF will be read on site to indicate treatment.

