	
standard finger stick microscopic.
 
 
• In the SSAT arm at enrollment, only children who are Pv seropositive and/or LMF Pv/Po positive receive supervised high-dose primaquine (1mg/kg for 7 days) regardless of their symptoms. All blood slides will be processed and read directly after blood collection. Then treatment will follow if positive. Sero-positive children, on the other hand, will commence treatment after the result is available (approximately 1 week). Symptomatic or asymptomatic LMF positive for Pf/Pm will be treated according to current national guidelines.
 
• In the control arm at enrollment, only children who are symptomatic and LMF Pv/Po positive will receive supervised high-dose primaquine (1mg/kg for 7 days).
 
• In both arms at every other timepoint, symptomatic LMF positive children will receive treatment in accordance with national guidelines (unsupervised).
 
• In both arms at the final timepoint, LMF will be conducted on all children and if positive will be treated according to national guidelines.
 
• As blood schizontocides, DHA-PP for 3 days will be given according to body weight (national guidelines).
 

Inclusion and Exclusion Criteria
	
Inclusion:
 
 
• resident of study area and attending selected elementary school in Grade 1-5
 
• no evidence of health condition that would interfere with study participation
 
• assent of child and documented parental informed consent
 
 
Exclusion:
 
 
• G6PD deficiency as determined by SD Biosensor quantitative determination of <70% G6PD activity (male: <4 U/g Hb, female: <6 U/g Hb).
 
• Haemoglobin < 9 g/dL
 

Analysis plan and sample size calculation
	
The study is designed to show a superiority of SSAT vs. routine care for the prevention of recurrent P. vivax infections. The primary study endpoint will be the proportion of children with recurrent P. vivax by PCR during 9 months of follow-up. Secondary endpoints include time-to-first P. vivax recurrence as well as incidence of symptomatic

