### **7.3. Blood smear Giemsa staining and microscopic reading**

Blood films will be dried in room temperature overnight, and fixed with methanol (thin smear only) before it is stained using 3% Giemsa made by mixing the stock solution with buffer. The stain will be gently poured into the slides until they are totally covered. After 45-60 minutes, slides will be rinsed with water and allowed to dry and read under binocular microscope with 1,000 magnification (20).

WHO certified microscopist will read the slides in the field, and cross check will be done at Jakarta. Asexual stages and gametocytes will be counted separately. For LMF, parasites will be counted against leucocytes in the thick smear. Density will be recorded as the number of parasites found per 200 leucocytes. A conversion to number of parasites in microliter of blood will be conducted under the assumption of one microliter of blood contains 8,000 leucocytes.

For LMS, parasites will be counted against RBC found in 20 HPF. Density will be recorded as number of parasites per 1 microliter. A conversion to number of parasites in microliter of blood will be conducted under the assumption of one microliter of blood contains 5,000,000 RBC.

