## **8. Data management and analysis**

### **8.1. Data management**

Qualitative and quantitative data will be collected during study period. Research team will visit selected elementary schools to conduct demographic census of study participants with the assistance of class teacher and cadres.

[figure not shown]
Body weight and temperature, history of fever, results of malaria examination and other substudies, anti-malarial treatment, AE, SAE (if any) will be recorded in Case Report Forms. CRF will only contain ID number of the subjects instead of their full name. Labelling of specimen will be given by adding activity number to the subject ID, e.g. QQxxx-0 (enrollment), QQxxx-1 (follow up 1), etc. (QQ=school initial, xxx=subject number)

After end of study, hard copy files will be stored for at least 5 years at UIOCRL. All CRFs will be transferred into electronic database. Only authorized individuals using secure, authorized computers may access this data management system.

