*Plasmodium* gametocytes prevalence in LMF and LMS will be calculated as the number positive for gametocytes by each diagnostic method divided by the number of subject examined. Diagnostic performance will be derived using  $2 \times 2$  contingency to determine sensitivity, specificity, positive predictive value (PPV), negative predictive value (NPV). Results of qPCR detection will be used as the gold standard for diagnostic method evaluation. All statistics will be reported as absolute values with their 95% confidence interval (95% CI). To assess the significance of different results of LMF and LMS methods, we will apply McNemar's chi-square test on  $2 \times 2$  contingency tables derived from the results of each detection method.

We will evaluate durability analysis by measuring population half-life of the existence of *Plasmodium* gametocyte detected by LMS samples. Gametocyte prevalence-based approach will use data on the appearance and disappearance of any circulating gametocytes according to the prevalence at month 0 and the prevalence at the time when they are fully cleared from skin vasculature.

Sensitivity, specificity, positive predictive value, and negative predictive value of hemozoin detection will be reported using microscopic Giemsa examination as golden standard.

Hemoglobin measurement using Sahli method and Standard G6PD will be compared to HemoCue by t test.

Hemoglobinopathy rate will be reported as descriptive value.

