**FORM SCREENING**

**SEKOLAH :** \_\_\_\_\_ **KELAS :** \_\_\_\_\_

**TANGGAL :** \_\_\_\_\_

No	ID	Nama	L/P	Usia	BB	Suhu	Demam seminggu terakhir	Serologi	Mikroskopik

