**FORM FOLLOW UP**

**SEKOLAH :**

**ID :**

**KELAS:**

**USIA:**

**NAMA:**

**L/P**

Kohort	Tgl	BB	Suhu	Demam seminggu terakhir (Y/T)	LMF	LMS	qPCR
1							
2							
3							
4							
5							
6							
7							
8							
9							
Di luar jadwal							
Di luar jadwal							
Di luar jadwal							

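### Nothing in the protocol keeps the ankle-smear (LMS) reading independent of the finger-smear and qPCR results it is compared with, so LMS accuracy, LMS gametocyte duration and the LMS-LMF test are open to review bias

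*Protocol*

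**What the plan says.** **Order of reading.** The Study Synopsis says of enrolment: "All blood slides will be processed and read directly after blood collection", with treatment following a positive result. Section 6.10 says of the ankle smears taken at enrolment: "Malaria status by LMS will be assessed post-hoc and will not indicate any treatment".

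**Reader.** Section 7.3 has one sentence for both smear types: "WHO certified microscopist will read the slides in the field, and cross check will be done at Jakarta". It then gives the counting rules for LMF and LMS. It mentions no masking, recoding or separate reader.

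**Label.** Section 8.1: "Labelling of specimen will be given by adding activity number to the subject ID". Specimens taken from one child at one visit thus share one key.

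**Forms (Appendix J).** The follow-up form is one page per child, headed by ID and name, with one row per visit. Its last columns are "Demam seminggu terakhir (Y/T) LMF LMS qPCR", that is, fever in the past week followed by the three test results. The household form also sets LMF beside LMS. The enrolment form, "FORM SCREENING", has serology and microscopy columns but none for LMS or qPCR.

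**Use of the results.** Endpoint VIII scores LMS against LMF and PCR. Endpoint IX is gametocyte duration in LMS and LMF. Section 8.3 takes qPCR as the reference standard and adds: "To assess the significance of different results of LMF and LMS methods, we will apply McNemar's chi-square test".

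**The concern.** Sensitivity, specificity and a paired comparison mean what they say only if each test is read without knowledge of the other. Reading a thin smear for scarce parasites involves judgement. A reader who knows that the finger smear was positive may search the ankle smear again. A reader who knows that it was negative may dismiss a doubtful object. The first habit raises LMS sensitivity and agreement with LMF. The second removes LMS-positive/LMF-negative slides, the very results that would support the skin-reservoir hypothesis in section 4.

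Endpoint IX is exposed in a similar way, because the follow-up form stacks a child's monthly results on one page.

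This is more than a detail that could be left to the analysis plan. The protocol itself fixes the labelling and the form, and no analysis can restore independence once slides have been read with the comparator in view.

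**Working it through.** The protocol gives no sample size, precision or power for the LMS endpoints, so there is no stated figure to reproduce. The check has two parts: what the text allows, and how large the effect could be.

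**1. What the text allows, by visit**

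| Visit | LMF and LMS paired? | Route by which LMS could be influenced |
|---|---|---|
| Enrolment | All children | LMF already read and acted on; slides carry the subject ID. The form has no LMS or qPCR column. |
| Months 1-8 | Symptomatic children only (section 6.7) | LMS shares a form row with fever, LMF and qPCR, but most LMF cells would be empty |
| Month 9 | All children | Same shared row, now with LMF for everyone |

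Appendix H marks LMF at every follow-up visit without a symptom condition. I follow sections 6.7 and 7.1.1, which restrict it. The two routes differ: reading order and labelling at enrolment, the shared row at follow-up. No section closes either.

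**2. Possible size: up-calling only**

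Inputs: 800 children and about 20% PCR-positive (section 8.2) give 800 × 0.20 = 160. The remaining inputs are assumptions, since the protocol gives none: LMF sensitivity 40%, true LMS sensitivity 30%, half of the LMS positives also LMF-positive.

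- LMF-positive: 160 × 0.40 = 64. LMS-positive: 160 × 0.30 = 48. Both: 24.
- LMF+/LMS−: b = 64 − 24 = 40. LMF−/LMS+: c = 48 − 24 = 24.
- McNemar: χ² = (b − c)²/(b + c) = 16²/64 = 4.00, p = 0.046. The exact p is 0.060 and the continuity-corrected p is 0.061.

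Suppose a share r of the 40 LMF+/LMS− slides is re-called LMS-positive:

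| r | Re-called | Apparent LMS sensitivity | b vs c | χ² | p (uncorrected) |
|---|---|---|---|---|---|
| 0 | 0 | 48/160 = 30.0% | 40 vs 24 | 4.00 | 0.046 |
| 10% | 4 | 52/160 = 32.5% | 36 vs 24 | 2.40 | 0.12 |
| 20% | 8 | 56/160 = 35.0% | 32 vs 24 | 1.14 | 0.29 |
| 30% | 12 | 60/160 = 37.5% | 28 vs 24 | 0.31 | 0.58 |

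**3. Adding the opposite habit**

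Keep the 8 up-calls and also let the reader discard some of the 24 skin-only positives.

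- Discard 5: 32 vs 19, χ² = 13²/51 = 3.31, p = 0.069. LMS sensitivity is (56 − 5)/160 = 31.9%.
- Discard 8: 32 vs 16, χ² = 16²/48 = 5.33, p = 0.021 (exact 0.029). LMS sensitivity is (56 − 8)/160 = 30.0%, its true value, although 16 slides have been miscalled.

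**4. When the two methods are truly equal**

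A simulation gave both methods 30% sensitivity with independent errors in 160 PCR-positive children (exact McNemar test, 2,000 runs per setting). Apparent LMS sensitivity is 0.30 + 0.30 × 0.70 × r.

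| r | Apparent LMS sensitivity | Rejection rate, no true difference |
|---|---|---|
| 0 | 30% | about 4% |
| 10% | 32% | about 6% |
| 20% | 34% | about 11% |
| 30% | 36% | about 24% |

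Across parts 2 and 4, r of 10-30% adds 2.1 to 7.5 percentage points to apparent LMS sensitivity. The McNemar test can lose a real difference, regain it, or show a false one.

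**The case against.** The strongest reply is that the point rests on silence. A label with subject ID and visit number carries no result. Form columns show where results are collated, not what a microscopist sees. No section says that the LMS reader holds the form or a result list, and masking could sit in a laboratory procedure. Section 7.3 also requires a certified microscopist and a Jakarta cross-check. This stands in part: actual access is not shown. But certification and a cross-check are not masking, and where the protocol does specify order, labels and forms, each leaves the comparator within reach.

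Three stronger readings are tempting and not supported.

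- *LMS is read with the qPCR result in hand.* qPCR is done in a Jakarta laboratory, and Appendix C shows only that PCR runs in the same months as sampling. Nothing says that it is entered before LMS is read.
- *The deferred reading and the shared row affect the same slides.* The deferral sentence concerns enrolment, whose form has no LMS or qPCR column. The shared row belongs to follow-up. The sentence may also mean only that LMS does not guide treatment.
- *Unmasked reading would make a real LMS-LMF difference vanish.* The move from p = 0.046 to 0.29 uses assumed inputs. Its baseline is about 0.06 by the exact test, and it reverses when enough skin-only positives are also discarded.

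Nor does the protocol show that a positive call usually rests on a single object: the 20 fields in section 7.3 are a rule for density, not a stated rule for positivity.

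**Conclusion.** The concern holds as a risk of review bias in secondary endpoints VIII and IX and in the LMS-LMF McNemar test. It arises from reading order and ID-labelled slides at enrolment, and from the shared form row at follow-up, chiefly at month 9. It is not evidence that any reader sees the other results.

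The size and direction are undetermined. The range of roughly 2 to 8 percentage points in apparent LMS sensitivity assumes 160 PCR-positive children, 30% true LMS sensitivity and 10-30% re-calling of LMF+/LMS− slides, with no discarding. Of these inputs only the 20% prevalence and the 800 children come from the protocol. The primary endpoint rests on PCR and genotyping, and LMS triggers no treatment, so neither is affected. The change should be made because it is cheap and works only if it is in place before the slides are read.

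**What to change.** In sections 6.10 and 7.3, with a matching line in 8.1:

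- Label each LMS slide with a code that does not reveal the subject ID or link visits of the same child.
- Have the existing readers, and the Jakarta cross-check, read LMS masked to LMF, qPCR, hemozoin detection (MOD), symptoms and arm.
- Record LMS on a separate sheet and remove its column from the shared follow-up row.
- Link LMS results to the subject only after the LMS reading is locked.

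Readers, slides and sample size stay the same. The cost is relabelling, a code list and one extra sheet to maintain. A sentence stating that LMS readers are masked would be a minimum, but ID-based labels and the shared row would make it hard to keep to.
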